Comparison of Endovascular and Open Repair of Juxta- and Pararenal Abdominal
Aortic Aneurysm on Short- and Long-term Clinical Outcomes

NCT ID not yet assigned

Date of the document: 1st January 2021

A Note from the Investigator

Dear Collaborator,

On behalf of all project collaborators, welcome! We are very excited to be working with you to investigate whether there is a difference in terms of short-/long-term outcomes of open versus endovascular treatment for juxta-/pararenal abdominal aortic aneurysm (AAA). Thank you for committing to participate in this project.

This document has been prepared to assist you and your team in preparing your Institutional Review Board (IRB) submission. In the sample proposal, you will find information that IRBs commonly request in their review of prospective observational studies that qualify for expedited review. We understand that every IRB has a unique application and varied review process; please use your discretion to modify the sample and accommodate the needs of your IRB.

We are available to provide any additional information that your IRB may request. Please do not hesitate to contact [name] via email at [contact] if you need additional assistance or have any questions.

We look forward to working with you.

Sincerely,

[name] MD and [name] MD Ph.D., principal investigators.

Project Title

Comparison of Endovascular and Open Repair of Juxta and Pararenal Abdominal Aortic Aneurysm on Short and Long-term Clinical Outcomes

Keywords

Abdominal aortic aneurysm (AAA)

Juxtarenal AAA - AAA where the neck is shorter than 1cm

Pararenal AAA - AAA where the aneurysm involves at least one renal artery orifice

Endovascular repair

Open repair

Short-term outcomes

Long-term outcomes

Background and Significance

Endovascular abdominal aortic aneurysm repair (EVAR) has gained a widespread acceptance in the treatment of patients with abdominal aortic aneurysm (AAA). Prospective randomized trials (RCTs) have demonstrated several short-term advantages over open repair such as less blood loss, operative time, hospital stay, morbidity and mortality [1-3]. The applicability of EVAR is limited by the presence of inadequate neck or involvement of the visceral arteries. Thus consequently open AAA repair is now being performed primarily for complex aortic anatomy, such as juxtarenal and pararenal aneurysms.

Open repair remains the gold standard for fit patients with complex AAA [4-6]. In the past decade, an evolution of devices, design, components and delivery systems expanded the application of EVAR in these challenging anatomies. Fenestrated stent-grafts are now commercially available for the repair of complex AAA in the United States and Europe. Initial reports have demonstrated high technical success rate, low renal dysfunction rate and low morbidity and mortality with promising short- and long-term results [7-10]. Other reports have shown excessive morbidity and mortality with fenestrated EVAR (FEVAR) [11].

Studies comparing endovascular and open repair are sparse, especially when it concerns long-term outcomes. There are till nowadays only two propensity score matched studies, one showing worse short-term and another long-term clinical outcomes for fenestrated-branched EVAR (F/BEVAR) over open surgical repair (OSR) [11,12].

Vascular surgeons are therefore left with a paucity of data to guide decision-making.

Study objectives:

1. Primary aims

a. Compare Kaplan-Meier freedom from aortic related reintervention rate between endovascular and open repair group

Primary endpoint: Kaplan-Meier aortic related reintervention rate at last follow-up

b. Compare Kaplan-Meier mortality rates between two study groups

Primary endpoint: Kaplan-Meier survival rate at last follow-up

3. Secondary aim: compare short term outcomes in terms of 30-day complications rate, especially acute kidney injury according to the RIFLE criteria [13]

Secondary endpoint: 30-day complications rate, especially acute kidney injury according to the RIFLE criteria [13]

Study design

Subject selection

Inclusion criteria:

- All patients (over 18 years of age) with a history of juxta- and pararenal AAA repair from January 2011 to January 2021
- All management strategies will be included (endovascular and open)

Exclusion criteria:

- Patients who are pregnant
- Patients who are under 18 years of age
- Patients who have ruptured AAA
- Patients with thoracoabdominal aortic aneurysm (ThAAA)
- Patients who have a mycotic AAA
- Patients with connective tissue disorder

Sample size: To ensure sufficient statistical power to answer hypothetical questions, approximately 700 subjects will be entered into the database.

Aortic-related reintervention rate is the primary end point being used to calculate sample size. Assuming a difference of 7% in the late reintervention rate between endovascular and open repair, 221 patients would be required in each arm to achieve a statistical power of 85% at

$p=0.05$. With two arms (endovascular versus open), assuming a 20% rate of missing data, a total N of 550 patients is required.

Research Design

This is a prospective study with patients treated for juxta- and pararenal AAA from 2011 through 2021 treated at six different vascular surgery centers:

1. Clinic for Vascular and Endovascular Surgery Belgrade
2. Department of Vascular Surgery, Policlinico S. Orsola-Malpighi, Bologna, Italy
3. Department of Vascular Surgery, San Raffaele Hospital, Milan, Italy
4. Department of Vascular Surgery, Dijklander Ziekenhuis, Hoorn, Netherlands
5. Department of Vascular Surgery, Amsterdam Univeristy Hospital, Amsterdam, Netherlands
6. Department of Vascular Surgery, Helsinki University Hospital, Helsinki, Finland

Procedures Involved

The study does not involve any patient contact and will not impact the care that patients receive. Data regarding the patients will be compiled and analyzed to accomplish the proposed study objectives. Data collection will include demographic information, patient-related factors and comorbidities, diagnostic imaging information, laboratory data, surgical procedure information, complications of surgery and outcomes.

Multi-Institutional research

After the data has been collected at a participating institution, the data will be transmitted to a central analytic center located at the Clinic for Vascular and Endovascular Surgery/Clinical Center of Serbia/Medical Faculty, University of Belgrade.

Risks and Benefits

Risks to Subjects

As this is a prospective observational cohort study, there is no potential for physical risks to subjects. There is a minimal risk of breach of confidentiality that could occur when patient information is collected and analyzed for the proposed study. However, appropriate measures will be taken to minimize the risk as much as possible. All information recorded will be de-identified. This study will abide by all regulations related to protecting human subjects and protected health information.

Potential Benefits to Subjects

There is no direct benefit to the subjects. However, future patients with juxta- and pararenal AAA may benefit from improved care as a result of this study.

Statistics and Data Analysis

Continuous variables will be described using the median and interquartile range or mean and standard deviation. Categorical variables will be described using frequencies and percentages. Group comparisons will be performed by using the Student t-test or Mann-Whitney U test, as appropriate. Categorical data will be expressed as percentages and were compared using the chi-square test or Fisher exact test. Propensity score analysis will be performed by matching endovascular to open surgery group in 1:1 ratio controlling for demographics, baseline comorbidities and AAA parameters. Differences will be considered statistically significant at $p < 0.05$. The cumulative incidences of all cause mortality and aortic-related complications will be estimated using the Kaplan-Meier method. Differences between curves will be tested using the log-rank test. Analyses will be done with SPSS software, version 20.0 (SPSS, Chicago, IL, USA).

Conflict of Interest

The investigators have no conflict of interest to report.

Funding Source

There are no plans to apply for grants or additional funding. No funding is required for the completion of this study.

Publication Plan

All research personnel listed on this protocol will be eligible for authorship in any resulting abstracts and publications in accordance with the qualifications outlined by the International Committee of Medical Journal Editors. The order of authors will be determined prior to manuscript development and depend on each individual's contribution to the study.

References

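### The Kaplan-Meier reintervention endpoint has no rule for deaths; if deaths are censored, the reported rate in each arm exceeds the share of patients who have a reintervention

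*Combined protocol and SAP*

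**What the plan says.** Under Study objectives, primary aim (a) is "Compare Kaplan-Meier freedom from aortic related reintervention rate between endovascular and open repair group", with the endpoint "Primary endpoint: Kaplan-Meier aortic related reintervention rate at last follow-up". Aim (b) is mortality, with the endpoint "Primary endpoint: Kaplan-Meier survival rate at last follow-up". Both are therefore time-to-event outcomes read at last follow-up, with no fixed horizon. The cohort is patients "with a history of juxta- and pararenal AAA repair from January 2011 to January 2021".

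The sample-size text bases the study on reintervention: "Aortic-related reintervention rate is the primary end point being used to calculate sample size".

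The only description of time-to-event methods is in Statistics and Data Analysis: "The cumulative incidences of all cause mortality and aortic-related complications will be estimated using the Kaplan-Meier method", followed by "Differences between curves will be tested using the log-rank test". That section names aortic-related complications, not reintervention. The document contains no censoring rule, no competing-risk method and no statement on deaths before reintervention.

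**The concern.** Reintervention is a non-fatal event, and a patient who dies without one can no longer have one. The plan expects deaths, since it makes survival a primary endpoint. A Kaplan-Meier curve for reintervention needs a decision about those patients, and there are three possible ones:

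- **Censor at death.** One minus Kaplan-Meier then describes a hypothetical population in which nobody dies first. It is not a cumulative incidence, and it exceeds the share of patients who have the event whenever some die before it.
- **Count death as an event.** The curve becomes reintervention-free survival, which is a different endpoint.
- **Treat death as a competing event.** This gives the cumulative incidence, but the Kaplan-Meier estimator does not deliver it.

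The first is the usual practice and the natural reading, though it is not written. On that reading each arm's reported rate is too high as a statement of how many patients have a reintervention, and the excess grows with mortality by the time point. Aim (a) compares the two arms, so the gap that readers take from the two rates also shifts. If mortality differs by arm, it can shift in either direction. The Background says surgeons lack data to guide decisions; for that purpose the share of patients who actually have a reintervention is a natural figure to read.

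**Working it through.** **Inputs.** From the documents: a 7-point difference in late reintervention, 221 patients per arm, 85% power, significance level 0.05. Not in the documents, and therefore assumed: the rate in each arm, mortality by the time point (10% to 50%), and constant hazards.

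**The plan's own figure.** The text reads "Assuming a difference of 7% in the late reintervention rate between endovascular and open repair, 221 patients would be required in each arm", without the two rates. The pooled two-proportion formula, two-sided, is

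n = [1.960·√(2p̄(1−p̄)) + 1.036·√(p₁(1−p₁)+p₂(1−p₂))]² / (p₂−p₁)².

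With 3% and 10%, p̄ = 0.065 and n = (0.6833 + 0.3577)² / 0.0049 = 221.2 per arm. So 3% versus 10% is one pair that reproduces 221; other formulas reach about 221 from other low rates. At 10% versus 17% the same formula gives 426.4.

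**Kaplan-Meier rate against true share.** For a Kaplan-Meier rate k and mortality m by the time point, let R = −ln(1−k) and D = −ln(1−m). The cumulative incidence is

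CI = R/(R+D) × (1 − exp(−(R+D))).

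Example, k = 10% and m = 20%: R = 0.1054, D = 0.2231, R+D = 0.3285, so CI = 0.3207 × (1 − 0.7200) = 8.98%.

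| Mortality by time point | True share, k = 10% | True share, k = 3% | Relative overstatement |
|---|---|---|---|
| 10% | 9.50% | 2.85% | about 5% |
| 20% | 8.98% | 2.69% | about 11% |
| 30% | 8.44% | 2.53% | about 19% |
| 40% | 7.87% | 2.35% | about 27% |
| 50% | 7.26% | 2.17% | about 38% |

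In an arm of 221, a 10% rate reads as 22.1 patients. The expected number is 221 × 0.0898 = 19.8 at 20% mortality and 221 × 0.0726 = 16.0 at 50%.

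**Gap between arms.** By Kaplan-Meier every row below shows 7.0 points.

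| Kaplan-Meier rates, open vs endovascular | Mortality, open / endovascular | Gap in true shares |
|---|---|---|
| 3% vs 10% | 20% / 20% | 6.29 |
| 3% vs 10% | 50% / 50% | 5.09 |
| 3% vs 10% | 30% / 45% | 5.04 |
| 3% vs 10% | 30% / 50% | 4.73 |
| 3% vs 10% | 50% / 30% | 6.27 |
| 3% vs 10% | 50% / 10% | 7.33 |
| 10% vs 17% | 30% / 50% | 3.96 |
| 10% vs 17% | 50% / 30% | 7.12 |

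The 10% versus 17% rows do not fit 221 per arm and show direction only.

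**Sensitivity to hazard shape** (k = 10%, m = 30%; constant hazards give an excess of 1.6 points). With cumulative hazards for reintervention and death proportional to t^0.5 and t² (early reinterventions, late deaths), the excess is 0.6 points. With t² and t^0.5 it is 2.5 points. The size moves; the sign does not.

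**Simulation at the planned arm size.** 4,000 arms of 221 patients, administrative censoring uniform over 0–10 years, k = 10% and m = 30% at 5 years. Mean one minus Kaplan-Meier with deaths censored was 9.99% (SD 2.7 points). Mean Aalen-Johansen was 8.42% (SD 2.2 points), against a true share of 8.44%.

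**The case against.** The strongest reply has four parts.

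1. **The planned inference is untouched.** The plan has curves and log-rank tests, with no risk difference or confidence interval, and a log-rank test with deaths censored validly compares cause-specific hazards. This stands. The problem is confined to how the reported rates are read.

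2. **Net freedom from reintervention, read beside survival, is a coherent quantity that aim (a) names openly.** The cumulative-incidence label is attached to mortality and aortic-related complications, so it reaches reintervention only by inference. This stands in part. Kaplan-Meier may be kept, but only with the handling of deaths stated and without calling the result a cumulative incidence. The label is wrong as written for any non-fatal complication if deaths are censored.

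3. **The harm is conditional, and the figures have no anchor in the documents.** True: if death were an event, this bias would not arise, and the larger figures need 40–50% mortality. A 20-point mortality difference between matched arms is also an illustration, not a forecast. The omission itself is certain, and under censoring the direction of the per-arm bias is too.

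4. **The excess is smaller than the noise.** At 30% mortality the 1.6-point excess is below one arm's sampling SD of 2.7 points. It is systematic, however, and more patients do not remove it.

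**Conclusion.** The concern holds. The plan gives no rule for deaths in a primary endpoint. On the ordinary reading its stated estimator returns rates above the share of patients who have a reintervention. Under constant hazards the relative overstatement is about 5–11% at 10–20% mortality, which is small, and rises to about 38% at 50%. A 7.0-point Kaplan-Meier gap (3% versus 10%) corresponds to 6.3 to 5.1 points at equal mortality of 20% to 50%. With unequal mortality it can shrink further or widen slightly.

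All sizes rest on assumed mortality, assumed arm rates and constant hazards. Kaplan-Meier for all-cause mortality is correct, and neither log-rank test is affected. This should be fixed before analysis, but it does not undermine the planned comparison.

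**What to change.** In Statistics and Data Analysis, replace the sentence on cumulative incidences with text such as:

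> All-cause mortality will be estimated by Kaplan-Meier. The cumulative incidence of aortic-related reintervention (and of aortic-related complications, if analysed separately) will be estimated with the Aalen-Johansen estimator, treating death without the event as a competing event, and reported by arm with 95% CI at a time point fixed before analysis. For reintervention, groups will be compared by log-rank test with deaths censored, described as a comparison of cause-specific hazards. The log-rank test for all-cause mortality is unchanged.

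Reword aim (a) and its endpoint to match. If Kaplan-Meier freedom from reintervention is preferred, the minimum is to say that deaths are censored, not to call it a cumulative incidence, and to report the Aalen-Johansen estimate beside it. In either case, reconcile complications in the statistics section with reintervention in the objectives and sample-size text, so that the analysis names the primary endpoint.

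**Cost.** Wording changes in two sections and a little more analysis. No new data should be needed, because the survival endpoint already requires dates of death. Software other than the SPSS version named may be needed for the estimator. Reported reintervention rates will be lower than by Kaplan-Meier. With a fixed time point, later events drop out of the headline rate but still count in the log-rank test.

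### Both primary Kaplan-Meier rates are defined at last follow-up with no common time point or data cut-off, and the 7% planning difference carries neither arm rates nor a year

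*Combined protocol and SAP*

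**What the plan says.** Under Study objectives, Primary aims, the two endpoints are "Primary endpoint: Kaplan-Meier aortic related reintervention rate at last follow-up" and "Primary endpoint: Kaplan-Meier survival rate at last follow-up". The secondary endpoint does carry a time, 30 days; the primary endpoints carry none.

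Statistics and Data Analysis adds no time: "The cumulative incidences of all cause mortality and aortic-related complications will be estimated using the Kaplan-Meier method", and "Differences between curves will be tested using the log-rank test".

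The dates given concern the repair, not follow-up. The inclusion criteria take patients "with a history of juxta- and pararenal AAA repair from January 2011 to January 2021". Research Design says "This is a prospective study with patients treated for juxta- and pararenal AAA from 2011 through 2021". The front page reads "Date of the document: 1st January 2021". No minimum follow-up, visit schedule or data cut-off is stated, so follow-up could close at about the document date or run on for years.

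The Sample size text plans on the first endpoint: "Assuming a difference of 7% in the late reintervention rate between endovascular and open repair". It gives 221 per arm for 85% power at p = 0.05, and 550 in total after 20% missing data. It gives neither the rate in each arm nor the year that counts as late.

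**The concern.** A Kaplan-Meier rate is a number at a stated time, and here the time is missing. There are two ways to read the endpoint.

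- **Literal.** Each rate is read at the end of its own curve. Few patients are still at risk there, one late event can move the estimate by many points, and the two arms may be read at different times.
- **Loose.** The phrase means that all available follow-up is used. The curves and the log-rank test are then clear, but no particular rate has been named. Most repairs are already in the past, so the year to report could be picked once the curves are visible.

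Under either reading, the planning difference is not tied to a horizon. Log-rank power depends on the number of events, and the same 7 points imply very different event counts depending on the year they describe and on when follow-up closes.

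**Working it through.** **1. The plan's own figure.** The arm rates are not stated, so 221 cannot be derived from the stated inputs alone. Working backwards with two-sided α = 0.05 (z = 1.960), 85% power (z = 1.036) and an assumed pair of 3% vs 10%, the pooled two-proportion formula is

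n = [1.960·√(2·0.065·0.935) + 1.036·√(0.03·0.97 + 0.10·0.90)]² / 0.07² = 221.2, so 222 per arm.

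The unpooled version gives 219. The total is 442/(1 − 0.20) = 552.5, so 553, against the stated 550. The plan's figures therefore fit 3% vs 10%, but that pair is inferred. The same 7 points from other base rates give other sizes: 156 per arm for 1% vs 8%, 284 for 5% vs 12%, 427 for 10% vs 17%. The missing arm rates alone block this check, before any question of horizon.

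**2. Precision of the rate under the literal reading.** All hazards and cut-offs are assumptions: 221 identical patients per arm, reintervention 2%/yr, death plus loss 10%/yr (total exit hazard 0.12/yr), and follow-up uniform over 0–10, 1–11 or 3–13 years.

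- At risk at 5 years: 221 × (0.5, 0.6, 0.8) × e^(−0.60) = 61, 73 and 97 per arm.
- At risk one year before the maximum: 221 × 0.1 × e^(−0.12 × 9, 10 or 12) = about 7.5, 6.7 and 5.

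Simulated Kaplan-Meier estimates, with ranges over the three windows:

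| Between-arm difference, no true effect | At curve end | At 5 years |
|---|---|---|
| SD | about 13 points | 3.3 to 3.9 points |
| Median absolute gap | about 6 to 7 points | 2.1 to 2.6 points |
| Share of studies with a gap above 7 points | 43% to 48% | 3% to 7% |

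The curve-end distribution is heavy-tailed; an SD based on its interquartile range is about 9 to 10 points, still well above the 5-year value. Varying reintervention over 1–3%/yr and death plus loss over 5–15%/yr, the last row ranges over 22–60% against 0.2–15%. For survival (death 5–10%/yr, loss 1–3%/yr), the SD is 10.4–13.5 points at curve end against 4.2–5.8 at 5 years.

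**3. Is there a systematic false gap or a size problem?** With the same follow-up window in both arms, no true effect, and endovascular accrual tripling over the period, the mean curve-end gap is at most about 0.5 points and the log-rank test rejects in 4.8% to 5.1% of studies.

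**4. Log-rank power by the year attached to the 7 points.** Assume 3% vs 10%, constant hazards, 221 per arm and death plus loss of m = 0.10/yr. The hazard ratio is ln(0.90)/ln(0.97) = 3.46, with log 1.241. Schoenfeld's formula asks for 4 × (1.960 + 1.036)²/1.241² = 23.3, so 24 events.

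Expected events per arm with follow-up uniform over 0–10 years are 221 · h/(h+m) · [1 − (1 − e^(−10(h+m)))/(10(h+m))]. If the rates are 5-year rates, h = 0.00609 and 0.02107, which gives 4.9 + 16.2 = 21.0 events. Schoenfeld power is Φ(√21.0/2 × 1.241 − 1.960) = 81%; simulation gives about 75%, the approximation being optimistic with so few events.

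| 3% vs 10% taken as | Events, 0–10 yr | Simulated power | Events, 3–13 yr | Simulated power |
|---|---|---|---|---|
| 3-year rates | 34 | 92% | 48 | 98% |
| 5-year rates | 21 | 75% | 30 | 88% |
| 10-year rates | 11 | 45% | about 15 | about 61% |

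The result moves with the other inputs. For the 5-year reading, death plus loss of 5%/yr or 15%/yr gives 81% or 69% with 0–10 years of follow-up, and 94% or 82% with 3–13 years. The 10-year reading reaches 88% with 350 per arm (the approximately 700 planned subjects split equally, before any matching loss), 5%/yr and 3–13 years.

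**The case against.** The strongest reply is that the planned comparison is a log-rank test of whole curves, which needs no landmark. That stands. No section tests a curve-end gap or uses 7 points as a decision threshold.

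A reader might go further than the documents allow in four ways.

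- **That the 43% to 48% is a false-positive rate.** It is the spread of a descriptive readout under the literal reading, with assumed hazards. The test itself keeps its size.
- **That the endpoint wording biases the comparison toward one arm.** That would need a different maximum follow-up by arm, which the documents do not show.
- **That 221 per arm is wrong.** It agrees with 3% vs 10%. What cannot be done is to confirm that this pair was used, or to say what log-rank power follows from it.
- **That a 10-year reading can never reach 85%.** It falls short at 221 per arm with 10%/yr death plus loss, but not under every plausible input.

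It is also fair to say that the loose reading is mild: only the year quoted beside the test is open to choice. But the protocol names a rate, not a test, as its primary endpoint, and that rate is what readers will carry away.

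**Conclusion.** The point holds and should be fixed. That the horizon, cut-off and arm rates are absent is plain from the text; the sizes rest on assumed hazards and follow-up windows.

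Followed literally, the stated rule gives a between-arm difference with roughly three to four times the SD of one read at 5 years in the central scenario (about 13 points against 3 to 4). Followed loosely, it leaves the reported year open. Neither reading affects type I error. If hazards are not proportional, the log-rank result will also depend on how long follow-up runs, which is a further reason to state the cut-off.

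The 85% power cannot be checked, for two separate reasons. The missing arm rates block the two-proportion calculation. The missing year and cut-off block the log-rank power, which for one compatible pair of rates at 221 per arm runs from about 45% to 98%.

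**What to change.** Before the pooled outcome data are analysed:

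- Define both primary rates at one fixed time after repair, common to both arms. Five years is an example; another whole year would serve if chosen only from potential follow-up (repair date to cut-off) and numbers at risk.
- Report the between-arm difference at that time with a 95% CI and the numbers at risk.
- State the data cut-off date.
- Keep the log-rank test on all follow-up as the governing hypothesis test, and name the fixed-time difference as the primary effect estimate, so that it is clear which result decides if the two disagree.
- State the two planning rates behind the 7% at that horizon, and restate the power if log-rank power at 221 per arm is not 85%.

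This needs short edits to the objectives, the sample-size text and the statistics section, with no new data and no change of test. The costs are real but small. Events after the horizon no longer count in the primary rate, though they still count in the curves and the test. The restated power may be less favourable than 85%, so the 221 may need fresh justification. And because centres already hold many outcomes for past repairs, the horizon can be fixed only before pooled analysis, not before any outcome exists.

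### Both primary outcomes are compared by log-rank with no adjustment beyond 1:1 matching, and no balance measure is set, so imbalance left after matching can go unflagged and uncorrected

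*Combined protocol and SAP*

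**What the plan says.** The analysis plan is one paragraph, headed Statistics and Data Analysis in the combined protocol and SAP.

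- **Confounding control:** "Propensity score analysis will be performed by matching endovascular to open surgery group in 1:1 ratio controlling for demographics, baseline comorbidities and AAA parameters". No caliper, matching algorithm, balance measure or balance threshold is given.
- **Group comparisons:** "Group comparisons will be performed by using the Student t-test or Mann-Whitney U test, as appropriate" and "Categorical data will be expressed as percentages and were compared using the chi-square test or Fisher exact test". The criterion throughout is p<0.05; sidedness is not stated.
- **Descriptive summaries:** "Continuous variables will be described using the median and interquartile range or mean and standard deviation", with frequencies and percentages for categorical variables.
- **Outcomes:** "The cumulative incidences of all cause mortality and aortic-related complications will be estimated using the Kaplan-Meier method", followed by "Differences between curves will be tested using the log-rank test". There is no Cox, logistic or other covariate-adjusted model and no sensitivity analysis. The section does not say that the log-rank test is run in the matched set or that it allows for the pairing.

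Study objectives names two primary endpoints, aortic-related reintervention and survival, both by Kaplan-Meier at last follow-up. The log-rank test is the only stated comparison for such curves.

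**The concern.** Treatment was not randomised, and Background and Significance describes open repair as the standard for fit patients. The protocol itself thus suggests selection by fitness, which bears on survival. Matching is the only safeguard, so the plan should say how its success will be judged and what follows if it falls short. It does neither.

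The only available yardstick is a p-value. Its sensitivity depends on the number of pairs: as matching discards patients, a given imbalance becomes less likely to be significant although it biases the outcome just as much. Because the log-rank comparison includes no covariates, whatever imbalance remains is carried into both primary results.

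**Working it through.** **1. The plan's own sample size.** Sample size starts from "Assuming a difference of 7% in the late reintervention rate between endovascular and open repair", with 221 per arm and 85% power. No base rate is given. With a two-sided 0.05 test and pooled variance, an assumed 3% vs 10% gives 222 per arm, close to 221. For 20% missing data, 442/0.80 = 552.5, or 553, against the stated 550. So 221 per arm is a fair reference size. The number of matched pairs is not stated. If all of the roughly 700 patients split evenly and all matched, there would be 350 pairs, which is the upper limit.

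**2. Smallest observed imbalance that reaches p<0.05.** Assumptions: two-sided test, normal approximation, n per arm, pairing ignored, difference in SD units.

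Limit = 1.96 × √(2/n)

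| Pairs | Limit (SD) |
|---|---|
| 350 | 1.96 × √(2/350) = 0.148 |
| 221 | 1.96 × √(2/221) = 0.186 |
| 150 | 1.96 × √(2/150) = 0.226 |
| 100 | 1.96 × √(2/100) = 0.277 |

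The limit nearly doubles between 350 and 100 pairs. A fixed limit on the standardised mean difference (SMD) would not move.

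**3. Example.** A comorbidity at 38% vs 30% (assumed), 221 per arm:

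- z = 0.08 / √(2 × 0.34 × 0.66 / 221) = 0.08 / 0.0451 = 1.78, so p = 0.076 and the test does not flag it.
- SMD = 0.08 / √[(0.38 × 0.62 + 0.30 × 0.70)/2] = 0.08 / 0.472 = 0.17, above a 0.10 target.
- If the comorbidity doubled mortality (assumed), the ratio is biased by (1 + 0.38)/(1 + 0.30) = 1.38/1.30 = 1.06.

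**4. A second set of assumptions.** Take one continuous covariate with a hazard ratio h of 1.5 to 2.0 per SD and a residual SMD d of 0.10 to 0.186. The bias factor is about h^d, from 1.5^0.10 = 1.04 to 2.0^0.186 = 1.14. With E events, the true type I error of the log-rank test is about Φ(√(E/4) ln b − 1.96) + Φ(−√(E/4) ln b − 1.96), where b is the bias factor:

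- 100 to 200 events: about 0.055 to 0.15.
- 30 events: about 0.05 to 0.06.

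The documents give no event counts. At the assumed 3% vs 10%, 221 per arm would yield 221 × 0.03 + 221 × 0.10 = 28.7 reinterventions. On that assumption the reintervention test sits near the 30-event case, where the distortion is small.

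**The case against.** **The plan does not say that the t and chi-square tests judge balance.** This stands. The sentence on group comparisons precedes the matching sentence and does not say what is compared. A reader might infer that the plan will declare balance on the strength of non-significant p-values; the text describes no such step. What it supports is an omission: no balance diagnostic is stated. The limits in step 2 therefore apply only if those tests are put to that use.

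**Descriptive tables would show imbalance.** Largely right. A reader might infer that imbalance must pass unseen, but means, SDs and percentages reported by matched group would reveal a 38% vs 30% split and allow an SMD to be computed. Imbalance *can* pass unflagged. The plan gives no threshold or action once it is visible.

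**Matching is itself the adjustment.** Also right. A simple comparison within a matched set is a recognised marginal analysis, so it would be wrong to call the plan's comparison wholly unadjusted. The point is limited to what matching leaves behind.

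**The bias could be far larger.** A reader might compound the 6% over three or five covariates and reach 20% or 35% (1.38/1.30 cubed, or to the fifth power). That needs each covariate to be independent, to double mortality, to lean the same way and to sit at z = 1.78. With equal weights, the combined gap would be z = 1.78 × √3 = 3.1 or 1.78 × √5 = 4.0. Matching on the score is meant to remove such a gap, and even a p<0.05 test of the score would flag it. The documents do not support those figures.

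**A hard SMD limit for every variable is too strict.** This stands. At 221 per arm the chance standard error of an SMD is √(2/221) = 0.095, so a perfectly randomised covariate falls within 0.10 with probability 0.707. Ten independent covariates (an assumed number) would all do so with probability 0.707^10, about 3%. Matching can do better than chance, but 0.10 should be a target, not an absolute requirement.

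**Conclusion.** The point holds as a worthwhile improvement to the plan; it does not show that the primary comparison is invalid. Both primary outcomes are compared by log-rank with no adjustment beyond matching, and the plan has no stated way to recognise or correct imbalance that remains. If significance tests are used as the check, it misses observed differences up to about 0.15 SD in the best case and 0.19 SD at 221 pairs, and it weakens further as pairs are lost.

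The detection limits need only a two-sided 5% test and the number of pairs. The size of any bias cannot be derived from the documents: about 6% for one binary covariate, or a factor of 1.04 to 1.14 for one continuous covariate, rests on assumed prognostic effects. The 6% example concerns mortality, and no specific covariate effect on reintervention has been shown. The 0.10 benchmark is a convention and does not appear in the documents, but the argument applies to any fixed limit.

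**What to change.** 1. In the matched set, report SMDs for all variables in the propensity score against a pre-set target (for example 0.10). If important prognostic variables miss it, revise the score or the caliper before any outcome is analysed.
2. Keep Kaplan-Meier and log-rank, and state that they are run in the matched set. Alongside them, estimate the treatment effect by Cox regression (logistic regression for 30-day complications) in the matched set, adjusted for a short list of prognostic covariates named in advance, with variance that allows for the pairing. Naming the list beforehand keeps the model from depending on which variables happen to be imbalanced.

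**Cost:** SAP wording and a little more analysis. The covariates are already to be collected, so no new patients or data are needed. A tighter match may lose pairs, to be weighed against the 221 per arm required. The adjusted hazard ratio is conditional rather than marginal, so it should be labelled as such beside the unadjusted matched comparison.
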